## **10. CONCOMITANT MEDICATIONS AND PROCEDURES**

Concomitant medications and procedures will be summarized for the Weeks 0-12 placebo-controlled phase using the safety population, for the Weeks 0-52 and Weeks 0-104 apremilast-exposure periods using the apremilast subjects as treated population, and for the Weeks 52-104 apremilast-exposure period for subjects who receive at least 1 dose of apremilast after Week 52.

### **10.1. Concomitant Medications**

A concomitant medication in each of the above periods is defined as a non-study medication with any amount taken during the period as defined in Section 5.2.

The ATC coding scheme of the WHODD will be used to group medications into relevant categories. Concomitant medications will be summarized by ATC2 level and standardized medication name, with ATC2 levels and standardized medication names within each ATC2 level sorted in descending order of frequency.

### **10.2. Concomitant Procedures**

Concomitant procedures are defined similarly to concomitant medications. Concomitant procedures will be coded according to the MedDRA, and summarized by SOC and PT, with SOCs sorted in the standard international order and PTs within each SOC in descending order of frequency.

## 11. EFFICACY ANALYSIS

### 11.1. Multiplicity

Formal statistical tests, conducted at a 2-sided significance level of 0.1, are planned between APR 40 BID and placebo and between APR 30 BID and placebo for the primary efficacy endpoint. To control the family-wise Type 1 error rate at the 0.1 level, these 2 formal statistical tests will be carried out by using a fixed sequence testing procedure, with the comparison between APR 40 BID and placebo tested first. The comparison between APR 30 BID and placebo will be tested only if the comparison between APR 40 BID and placebo is statistically significant. If any of the 2 apremilast dose groups is discontinued prior to the end of the study, the treatment comparison will be conducted for the comparison between the retained apremilast dose and placebo at a 2-sided significance level of 0.1.

For formal statistical tests that are planned but not performed as a result of the aforementioned multiplicity adjustment strategy, as well as for any other comparisons that are not subjected to multiplicity adjustment, nominal 2-sided p-values (without adjustment for multiplicity) will be provided as a measure of the strength of association between the endpoint and the treatment effect rather than formal tests of hypotheses.

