Eligible subjects will enter the Double-blind Placebo-controlled Phase for 12 weeks, at the Baseline Visit (Week 0, Visit 2). Subjects will be randomly assigned to study treatment as described above. With the aim to mitigate potential dose-related side effects associated with apremilast, such as headache and gastrointestinal (GI) disturbances, apremilast-treated subjects will be dose-titrated in 10-mg/day increments over the first 8 days of treatment (Table 5). All subjects will receive blister cards of identical appearance to maintain blinding. Subjects will continue to receive the treatment assigned at baseline for 12 weeks.

Blinded Active-treatment Phase

Following 12 weeks of treatment, subjects will enter the Blinded Active-treatment Phase for 40 weeks. At the Week 12 visit, subjects will be evaluated for clinical improvement based on the TMS. The endoscopy subscore assessed by the investigator will be used for the calculation of the Week 12 TMS.

Subjects who achieve at least a 20% decrease from baseline in the TMS at Week 12 will receive the following IP between the Week 12 Visit and the Week 52 Visit:

- Subjects who were randomized to apremilast (30 mg BID or 40 mg BID) at baseline will continue to receive the treatment assigned at baseline.
- Subjects who were randomized to placebo at baseline will be re-randomized to receive apremilast (30 mg BID or 40 mg BID) and will be dose-titrated in 10-mg/day increments over the first 8 days of treatment (Table 5).

Subjects who do not achieve at least a 20% decrease from baseline in the TMS at Week 12 will receive the following IP until the Week 52 Visit:

- Subjects who were randomized to apremilast 30 mg BID at baseline will be re-assigned apremilast 40 mg BID, with no dose titration.
- Subjects who were randomized to apremilast 40 mg BID at baseline will continue to receive apremilast 40 mg BID.
- Subjects who were randomized to placebo at baseline will be re-randomized to receive apremilast (30 mg BID or 40 mg BID) and will be dose-titrated in 10-mg/day increments over the first 8 days of treatment (Table 5).

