4.1.3. External Safety and Efficacy Monitoring During Apremilast Program

Monitoring has been performed by an independent, external DMC assessing both safety and efficacy as outlined in the DMC charter. The DMC was comprised of 3 independent external trialists and an independent, external statistician, for whom there was no identified conflict of interest. The DMC was convened approximately every 6 months. Following the meeting with the DMC on 27 Oct 2017 the DMC continued to recommend that the study could continue as planned.

After all subjects completed the 12-week Placebo-controlled Phase, Celgene determined that the DMC was no longer necessary to support the CC-10004-UC-001 study since the safety profile of apremilast in UC is similar to that observed in the approved indications and no new safety signal emerged in CC-10004-UC-001.

[figure not shown]

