4.4. End of Trial

The End of Trial is defined as either the date of the last visit of the last subject to complete the study, or the date of receipt of the last data point from the last subject that is required for primary, secondary, and/or exploratory analysis, as prespecified in the protocol and/or the Statistical Analysis Plan, whichever is the later date.

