6.14. Study Completion

The End of Trial is defined as either the date of the last visit of the last subject to complete the study, or the date of receipt of the last data point from the last subject that is required for primary, secondary, and/or exploratory analysis, as pre-specified in the protocol and/or the Statistical Analysis Plan, whichever is the later date.

For the purpose of analysis, study completion for an individual subject is defined as reaching the Week 52 Visit. For subjects participating in the Extension Phase, completion of the Extension Phase for an individual subject is defined as completing the Week 104 Visit. Subjects not meeting this definition will be considered early termination subjects. All subjects are required to return for the Post-treatment Observational Follow-up Visit approximately 4 weeks after the last dose of IP.

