10.6. Efficacy Analysis

The ITT population (Section 10.2) will be the primary population for efficacy analyses. A supportive analysis using the PP population will also be performed for the primary efficacy endpoint.

The comparisons for the primary efficacy endpoint will be based on two-sided statistical tests at a significance level of 0.1. A hierarchical approach will be used to adjust for multiplicity. For the primary endpoint, the first test in the hierarchy will be the apremilast 40 mg BID treatment group compared to placebo, followed by the apremilast 30 mg BID treatment group compared to placebo. If any of the active treatment groups (apremilast 30 mg or 40 mg BID) is discontinued prior to the end of the study, the treatment comparison will be conducted for the retained treatment group vs. placebo based on a two-sided statistical test at the 0.1 level. Additional endpoints subsequent to the primary endpoint comparisons may be added to the hierarchy and specified in the SAP.

Summary of all efficacy endpoints over time will be provided using frequency and percent for categorical endpoints and descriptive statistics for continuous endpoints.

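### The dropped-dose clause (SAP 11.1, protocol 10.6) is not limited to drops before the Week 12 readout, so as worded it can conflict with the fixed-sequence gate that protects the 0.1 family-wise error

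*SAP*

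**What the plan says.** SAP 11.1 plans two formal tests of Week 12 clinical remission, each at two-sided 0.1, in a fixed sequence with 40 mg BID first. The gate reads: "The comparison between APR 30 BID and placebo will be tested only if the comparison between APR 40 BID and placebo is statistically significant". The stated aim is a family-wise Type 1 error of 0.1.

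The next sentence begins "If any of the 2 apremilast dose groups is discontinued prior to the end of the study, the treatment comparison will be conducted" and gives the retained dose a comparison with placebo at two-sided 0.1. In protocol 10.6 the same rule applies when either active group "is discontinued prior to the end of the study, the treatment comparison will be conducted for the retained treatment group vs. placebo". Neither text gives a condition on the reason for the drop, on its timing relative to the Week 12 analysis, or on what happens if 40 mg has already failed.

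The SAP section closes with a rule on tests that the sequence blocks: "For formal statistical tests that are planned but not performed as a result of the aforementioned multiplicity adjustment strategy", only nominal p-values are reported, as a measure of strength of association.

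On timing, protocol 10.1 and SAP section 2 place the placebo-controlled analysis when all subjects have completed the 12-week phase, followed by a Week 52 analysis and a final analysis. Protocol 4.4 says: "The End of Trial is defined as either the date of the last visit of the last subject to complete the study", or the last required data point if that is later.

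**The concern.** A fixed sequence controls the error only because the second test is closed once the first fails. The dropped-dose clause is a second route to a formal 30 mg test, and its only limit is the end of the study. Week 52 is 52 − 12 = 40 weeks after the Week 12 visit, and Week 104 is 104 − 12 = 92 weeks after it. A decision to discontinue the 40 mg group in that interval, with the Week 12 results in hand, would fit the words. SAP 11.1 would then give two answers for the same data: the gate and the nominal p-value rule make 30 mg descriptive, and the clause makes it a formal test at 0.1.

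At stake is the status of a 30 mg remission result with p ≤ 0.1 when 40 mg has failed: a formal finding, or a nominal p-value.

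**Working it through.** **Inputs from the documents.** Two-sided 0.1 per test (SAP 11.1); 1:1:1 allocation, 55 per arm (SAP 4.3); 49 per group before dropout, 30% versus 10% remission, 10% dropout (SAP 4.4). **Assumed:** no treatment effect in either dose, with remission 10% in every arm (the planned placebo rate), varied from 5% to 20%.

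**Reproducing the plan's figure.** n = [1.645·√(2·0.2·0.8) + 0.842·√(0.3·0.7 + 0.1·0.9)]² / 0.2² = 48.4, so 49; power at 49 is 0.804. Then 49/0.9 = 54.4, so 55 per arm and 165 in all. The plan's figures are reproduced with the uncorrected two-sided chi-square, which is used below.

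**Formulae.** With y placebo remissions (probability f(y)), let q(y) be the chance that one dose gives |z| > 1.645. The two doses are independent given y.
- 40 mg rejects (the fixed sequence makes a false claim exactly when this happens): Σ f(y)·q(y).
- Either dose rejects (30 mg formally tested after every failed 40 mg test): Σ f(y)·[1 − (1 − q(y))²].

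**Exact results, 55 per arm, two-sided:**

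| Null remission rate | 40 mg test alone | Either dose (ceiling) |
|---|---|---|
| 5% | 0.121 | 0.209 |
| 10% | 0.103 | 0.178 |
| 15% | 0.098 | 0.170 |
| 20% | 0.097 | 0.170 |

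The 5% row needs care: its single-test error is already 0.121 because the chi-square approximation is poor there, so not all of the excess over 0.10 comes from the clause. At 49 per arm and 10% the pair is 0.104 and 0.180.

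**Cross-checks.** A bivariate normal with correlation 0.5 (shared placebo, equal arms) gives a ceiling of 0.1755. A simulated stratified CMH test at 10% (400,000 trials, four assumed strata of 21/14/39/26%) gives 0.101 and 0.177.

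**Between the limits.** If the clause were used after a share s of failed 40 mg tests, independently of the 30 mg result, the error is 0.103 + s·(0.178 − 0.103). For assumed s of 10%, 25% and 50% this is about 0.11, 0.12 and 0.14. If use depended on the 30 mg result, the error could be higher for the same s, but never above the ceiling.

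**Drop before unblinding, unrelated to efficacy.** One full-level test remains, so the error is 0.103, with no inflation.

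**Drop before unblinding, guided by efficacy.** Suppose the dose with fewer remissions is dropped at 14, 27 or 41 of 55 per arm (about 25%, 50%, 75%; assumed timings) and the other is tested at 55 per arm. Exact two-sided error is 0.098, 0.096 and 0.096, within the stated 0.1. The one-sided chance of a false superiority finding is 0.069, 0.076 and 0.081, against 0.052 for a single test.

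**The case against.** The strongest reply is that the clause was never meant to work this way. It describes a comparison still to be made, and the only formal comparisons are at Week 12. After that visit placebo ends: "Subjects who were randomized to placebo at baseline will be re-randomized to receive apremilast". Once the Week 12 tests have been run there is no formal placebo comparison left to conduct, and a reading that contradicts the sentence just before it is a poor one. This is probably the intent, and under it the error stays at about 0.10. It does not close the gap, because the Week 12 data can be tested or re-labelled as formal at any later date, and neither text says which rule governs. The SAP sets an explicit limit elsewhere: section 5.4.2 fixes the per-protocol population before unblinding for this same analysis.

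Three further points stand in whole or in part.
- The figure of 0.18 belongs to a procedure that no passage prescribes. It is a ceiling.
- The definition of completion in protocol 6.14 ("For the purpose of analysis, study completion for an individual subject is defined as reaching the Week 52 Visit") concerns individual subjects and is weak evidence for what the end of the study means. The argument rests on protocol 4.4.
- A ban on efficacy-guided drops is not required by the stated two-sided 0.1. Protocol 4.1.3 says "Monitoring has been performed by an independent, external DMC assessing both safety and efficacy as outlined in the DMC charter", but the charter is not in the documents and may already restrict dropping a dose.

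A reader might also infer that the clause has been triggered, because Amendment 4 moves all Extension Phase subjects to 30 mg BID and protocol 1.4.3 credits 30 mg, but not 40 mg, with improvement in remission. The documents do not support this. The amendment is described as adjusting the Extension Phase dose, nothing equates that with discontinuing a randomized dose group, and section 1.4.3 reports no test result, so it does not show that 40 mg failed.

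**Conclusion.** The defect is in the wording, and it is real: a stated rule, read literally, can defeat the stated family-wise guarantee for the primary endpoint. The intended procedure holds the error at about 0.10 (exact 0.103). Under the literal reading the error lies between that and about 0.18 (exact 0.178), and the upper end needs 40 mg dropped and 30 mg formally tested after every failed 40 mg test. These figures assume no effect of either dose, 10% remission, 55 per arm and an unstratified chi-square; the CMH check agrees closely.

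It would be wrong to conclude that this trial's error rate is 0.18, or that the clause has been used. Neither is shown. The point deserves correction because it decides whether a 30 mg result can be formal, and because the correction is almost free.

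**What to change.** In SAP 11.1 and protocol 10.6:
1. Replace the end-of-study limit with one that requires the dose group to be discontinued before the database is unblinded for the Week 12 placebo-controlled analysis, the anchor already used in SAP 5.4.2.
2. Add that once the 40 mg test has been done and is not significant, 30 mg receives a nominal p-value only, whatever later happens to a dose group.

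Optional: also require that the drop was decided without comparative efficacy data. This is not needed for the two-sided 0.1, but it prevents the rise in one-sided false superiority from 0.052 to between 0.069 and 0.081, and SAP 11.3.1 frames the objective as superiority.

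The cost is two sentences, or three with the option. Sample size, test, alpha and testing order do not change. The downside is that a 30 mg result after a failed 40 mg test cannot be claimed as formal. Protocol 1.4.3 already reports Week 12 results, so the text should be dated and labelled as a clarification that only narrows what may be claimed.

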### 11.2. Missing Data Handling

#### 11.2.1. Treatment Failures

Subjects who have (1) protocol-prohibited initiation or dose increase of concomitant UC medications, or (2) a colectomy (partial or total) or an ostomy will be considered treatment failures after the date of the event. Use of antidiarrheals or dose increase of oral corticosteroids back to the baseline dose for subjects undergoing corticosteroid tapering will not be considered a treatment failure.

Efficacy data after the date of treatment failure will be considered missing. Of note, for efficacy analyses, the data after the date of treatment failure will be set to missing prior to the assignments of analysis time points as described in Section 5.3.1.

#### 11.2.2. Binary Efficacy Endpoints

##### 11.2.2.1. Primary Approach for Analysis

For binary efficacy endpoints, the primary approach to handling missing data will be nonresponder imputation (NRI), where subjects who have insufficient data for response determination for the time point under consideration will be considered nonresponders for that time point. Insufficient data, including missing data at baseline (if the binary endpoint assesses change from baseline) or a post-baseline time point, will be determined after the handling of time points as described in Sections 5.3.

#### **11.2.2.2. Sensitivity Analyses**

Sensitivity analyses using different missing data handling approaches (data as observed [DAO] and last observation carried forward [LOCF]) will be performed for the primary efficacy endpoint (clinical remission defined in the TMS) and the first secondary efficacy endpoint (clinical response defined in the TMS).

In the DAO analyses, only subjects with sufficient data for response determination at the time point under consideration will be included.

In the LOCF analyses, missing data at the time point under consideration will be imputed by the last post-baseline observation. For the TMS which consists of 4 individual subscores, the LOCF method will be applied to the individual subscores rather than directly to the TMS, and then the TMS will be calculated based on the observed or imputed subscores. Subjects who still have insufficient data for response determination at the time point under consideration despite the application of LOCF (eg, no post-baseline data) will be considered nonresponders for that time point.

#### **11.2.2.3. Approach for Descriptive Summary**

Binary endpoints by time point will also be summarized based on DAO, where only subjects with sufficient data for response determination at the time point under consideration will be included in the summary of that time point.

### **11.2.3. Continuous Efficacy Endpoints**

#### **11.2.3.1. Primary Approach for Analysis**

For continuous efficacy endpoints, the primary missing data handling approach will be last observation carried forward (LOCF). For subjects who initially receive placebo and switch to an apremilast dose at Week 12 and subjects who initially receive APR 30 BID and switch to APR 40 BID at Week 12, the values on or before the date of IP dispensing at Week 12 will not be carried over beyond Week 12. For the TMS, PMS, and MMS, which are composite scores derived from individual subscores, the LOCF method will be applied to the individual subscores rather than to the composite score.

#### **11.2.3.2. Approach for Descriptive Summary**

Continuous endpoints by time point will also be summarized based on DAO, where only subjects with sufficient data at the time point under consideration will be included in the summary of that time point.

## **11.3. Analysis of Primary Endpoint**

### **11.3.1. Primary Analysis of Primary Endpoint**

The primary objective of the study will be evaluated by testing the superiority of each of the 2 apremilast doses over placebo with respect to the proportion of subjects achieving a clinical remission in the TMS, defined as a TMS of  $\leq 2$ , with no individual subscore  $> 1$ , at Week 12 based on the ITT population and the Cochran-Mantel-Haenszel (CMH) test stratified by the randomization stratification factors. Within-group proportions, 2-sided 95% CIs (based on the

Wilson score method) for the within-group proportions, unstratified treatment differences in proportions, stratified treatment differences in proportions using the weighted average of the treatment differences across the strata with the CMH weights, stratified 2-sided 95% CIs (based on the stratified Newcombe method [Yan, 2010]) for the treatment differences in proportions, and the 2-sided p-values from the CMH tests, will be provided. Missing data will be handled by the NRI approach.

### 11.3.2. Sensitivity Analyses of Primary Endpoint

The following sensitivity analyses will be performed for the primary endpoint: 1) using the PP population and the NRI method for missing data; 2) using DAO (Section 11.2.2.2); 3) using the ITT population and the LOCF method for missing data (Section 11.2.2.2). The statistical methods adopted for the primary analysis will also be used for these sensitivity analyses.

## 11.4. Analyses of Secondary Efficacy Endpoints

The analyses of secondary efficacy endpoints will be performed identically to the primary analysis of the primary endpoint. In addition, the sensitivity analyses of the primary endpoint will also be performed for the first secondary efficacy endpoint (clinical response defined in the TMS).

[REDACTED]

## 12. SAFETY ANALYSIS

Safety will be evaluated via descriptive statistics and point estimates. No inferential testing for statistical significance will be performed.

The safety analyses will be based on the safety population for the Weeks 0-12 placebo-controlled phase, the apremilast subjects as treated population for the Weeks 0-52 and Weeks 0-104 apremilast-exposure periods, and subjects who receive at least 1 dose of apremilast after Week 52 for the Weeks 52-104 apremilast-exposure period. The treatment groups presented for these analysis periods are described in Section 5.2.

### 12.1. Adverse Events

AEs will be coded according to the MedDRA. Unless otherwise specified, AEs will be summarized by SOC and PT, with SOCs sorted in the standard international order and PTs within each SOC in descending order of subject incidence.

For the analyses of AEs, the following point estimates are provided, unless otherwise specified:

- Subject incidence: Subject incidence (i.e., percentage [%] used in a frequency summary) is defined as the number of subjects with the specific event divided by the number of subjects included in the analysis. Subjects with multiple occurrences of the specific event in the specific analysis period will be counted only once in the numerator.
- Exposure-adjusted incidence rate (EAIR) per 100 person-years: The EAIR per 100 person-years is defined as 100 times the number of subjects with the specific event divided by the total exposure time (in years) to the event among subjects included in the analysis. Subjects with multiple occurrences of the specific event in the specific analysis period will be counted only once in the numerator. The exposure time for a subject without the specific event is the duration of the specific analysis period as described in Section 5.2, whereas the exposure time for a subject with the specific event is the duration of the specific analysis period up to the start date (inclusive) of the first occurrence of the specific event. The total exposure time in years is calculated by dividing the sum of exposure time in days over all subjects included in the analysis by 365.25. The EAIR per 100 person-years is interpreted as the expected number of subjects with at least 1 occurrence of the specific event per 100 person-years of exposure to the event.

A subject data listing of all AEs (including treatment-emergent AEs [TEAEs] and non-TEAEs) will be provided.

